### The Handling of Study Interventions

The drug and placebo will be manufactured by Pfizer. Placebo has similar taste and color to the active drug. The drug and placebo will then be shipped to Rush University, and dispensed to the study team who will distribute them to the subjects as described above. The medication will be stored at room temperature in a climate-controlled room which will be secured by lock. The pills will be dispensed to the subjects in pill bottles. For the escalation phase, subjects will receive one pill of 0.5 mg daily for three days, then two pills daily for the next four days, then two pills of 1 mg for the remaining 56 days. Subjects will be asked to return any unused medication after nine weeks to Rush University. Study intervention accountability records will be completed according to the Manual of Operations. The subject, investigators, and study staff will be blinded to the treatment arm of each subject. The study team dispensing the drug and the independent medical monitor will disclose the randomization to the investigators after the database has been locked at approximately three months.

### Concomitant Interventions

Medications for neurological signs of Parkinson Disease must remain stable during the nine weeks of this study. The only contraindicated intervention is deep brain stimulation surgery.

- Required Interventions: oral varenicline 1 mg twice daily or placebo twice daily.
- Prohibited Interventions: concomitant use of trihexyphenidyl (Artane) or benztropine mesylate (Cogentin).
- Modifications to the study intervention can only occur during the open label escalation phase.

### Adherence Assessment

Adherence will be assessed by pill counts and adherence questionnaires that will be completed at each of the study visits. Because the study is using an intent-to-treat analysis, adherence will be reported using descriptive statistics.

### CLINICAL AND LABORATORY EVALUATIONS

#### Timing of Evaluations

Subjects will be consented and have initial laboratory studies and rating scales at the entry visit. Once on the study medication, they will be contacted by phone at three weeks for questions regarding side effects, clinical issues, and to answer any questions. The subject will be reassessed after five weeks for depression or suicidal ideation, and they will continue with the intervention or placebo. Again, they will be contacted by phone at week seven to assess for safety and tolerability. They will be seen at nine weeks and outcome measures will be performed.

Table 1. Timing of Evaluations

Evaluation	Screening	Entry	Week 3	Week 5	Week 7	Week 9
Informed Consent		X				
Documentation of PD	X					
Medical/Treatment Hx	X					
Inclusion/Exclusion	X					
Clinical Assessment		X				
Neurological Exam		X				
Adherence Assessments			X	X	X	X
Questionnaires						
MDS-UPDRS and other rating scales		X				X
Beck Depression/suicide scales		X		X		X
Mental Status exam		X				X
FAB		X				X
EKG		X				

#### Pre-Randomization Evaluations

These evaluations occur prior to the subject receiving any study interventions.

- Screening

At the screening visit, the diagnosis of Parkinson disease will be confirmed and medical history will be reviewed. Inclusion and exclusion criteria will be completed.

- Pre-Entry

Screening and pre-entry may occur concurrently. Consent will be obtained. EKG and blood tests will be completed at the visit and randomization will occur.

#### On-Study Evaluations

Blood chemistries, liver function tests, and hematology laboratory tests will be performed at two times during the study. Rating scales for movement disorders and cognitive disturbances will be performed twice during the study. The allowable time window is Schedule of Evaluations  $\pm$  7 days.

- Entry

The entry visit will occur at least two weeks after the screening visit to allow for adequate drug supply. Study drug will be dispensed at the entry visit.

- Intervention Discontinuation Evaluations

Evaluations done at the time of discontinuation include blood chemistry, hematology, and the rating scales. In addition, an adherence assessment will also be done.

- Post-Intervention Evaluations

Neurological examinations will be performed according to the standard of care by the treating neurologist/investigator.

- Final Evaluations

The final visit will consist of blood chemistry and hematology, neurological examination, rating scales (BBS, MDS-UPDRS, TUG, ABC, MMSE, FAB, BDI, and BSSI), and adherence assessment.

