## STUDY INTERVENTIONS

### Interventions, Administration, and Duration

42 subjects will be randomized to receive 1 mg twice daily of oral varenicline or matched placebo. The therapeutic dose will be escalated over the first week as 0.5 mg daily for three days, and then increased to 0.5 mg twice daily for the next four days. Thereafter, subjects will continue on 1 mg twice daily for the remaining eight weeks. The outcome measures will be assessed at the end of week 5 and then repeated at the conclusion of the study. Side effects will be monitored at each of the encounters with the subject, either in person or by telephone. The most common expected side effects include nausea, insomnia, abnormal dreams, or headache. Subjects will be evaluated in the outpatient Movement Disorders Clinic at Rush University at the initiation and conclusion of the study. All patients may remain on other medications for neurologic signs (with the exception of those mentioned in the exclusion criteria), but the dose of these medications must remain stable during the duration of the study.

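### The general ±7-day visit window lets the primary balance rating fall up to about a week after the last scheduled dose; closing its late side for the final visit is a cheap improvement

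*Combined protocol and SAP*

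**What the plan says.** - **Length of dosing.** The Handling of Study Interventions gives three days, then four days, "then two pills of 1 mg for the remaining 56 days". Interventions, Administration, and Duration agrees: after the escalation week, "subjects will continue on 1 mg twice daily for the remaining eight weeks".
- **End of the study period.** The Handling of Study Interventions adds: "Subjects will be asked to return any unused medication after nine weeks to Rush University". Concomitant Interventions says that background medication "must remain stable during the nine weeks of this study".
- **Primary rating.** Timing of Evaluations says of subjects: "They will be seen at nine weeks and outcome measures will be performed". On-Study Evaluations, under Final Evaluations, says: "The final visit will consist of blood chemistry and hematology, neurological examination, rating scales", and the BBS heads its list of scales.
- **Window.** On-Study Evaluations states: "The allowable time window is Schedule of Evaluations" ± 7 days. No narrower rule is given for the final visit.
- **Half-life.** The Rationale gives 24 hours.
- **Eight-week wording.** Interventions and Duration, the Primary Objective and the Secondary Objectives speak of eight weeks and do not say whether the escalation week is included.

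**The concern.** At the nominal visit, dosing and rating coincide. In the late half of the window they do not: a patient who took every scheduled pill and attended within the permitted window can still be rated days after the drug ran out. None of the sections cited extends dosing to cover a delayed visit or requires the BBS to be rated on drug.

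Placebo patients lose nothing by being rated late. Active patients lose whatever part of a balance effect depends on drug level, so the contrast can only move toward zero. A gap of this kind comes from scheduling, not from the treatment or the patient. The plan has little spare power to absorb it, because it is sized at 19 per group for 0.80.

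**Working it through.** **Timing.** Inputs: 3, 4 and 56 days (The Handling of Study Interventions); final visit at nine weeks (Timing of Evaluations); ±7 days (On-Study Evaluations); half-life 24 hours (Rationale).

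- Dosing: 3 + 4 + 56 = 63 days = 9 weeks. This agrees with the nine-week statements.
- Window: 63 − 7 = day 56 to 63 + 7 = day 70. Days 64 to 70 lie after the last scheduled dosing day.
- Counting whole days, the share of drug left on day 63 + k is 2^(−k): 50% on day 64 and 0.8% on day 70. The mean over the seven days is (1 − 2^(−7))/7 = 0.142.
- Dosing is twice daily, so a morning rating on day 64 after an evening dose on day 63 is only about 12 hours, or half a half-life, after the dose. That is close to the usual level before a morning dose. Measured against that level, the share left is 2^(−(k−1)): 100% on day 64, 1.6% on day 70, mean 2 × 0.142 = 0.283.
- If nine weeks means 63 days after a day-1 entry, the nominal visit is day 64 and the late limit day 71.

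Hence the range of roughly 0.5 to 7 half-lives. The first late day hardly matters; the later ones might.

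**The plan's own sample size.** With a difference of 8 points, SD 8.48 and two-sided 0.05 (Outcomes and Data Analysis), a two-sample t-test needs 18.65 per group for power 0.80, which rounds up to the stated 19. Power is 0.808 at 19 per group and 0.847 at 21 (all 42 analysed, equal allocation assumed).

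**Illustration of dilution.** Two inputs are not in the documents and are assumed: f, the share of final ratings made late, and r, the share of the effect left at a late rating. Late visits are taken as evenly spread over days 64 to 70. The diluted effect is 8 × (1 − f + f·r). For f = 0.10 and r = 0.142 this is 8 × (0.90 + 0.0142) = 7.31 points.

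| Effect left at a late rating | Late share | Effect (points) | Power, 19 per group | Power, 21 per group |
|---|---|---|---|---|
| any | 0% | 8.00 | 0.808 | 0.847 |
| 0.142 (tracks drug, whole days) | 5% | 7.66 | 0.773 | 0.815 |
| 0.142 | 10% | 7.31 | 0.735 | 0.778 |
| 0.283 (tracks drug, morning visits) | 5% | 7.71 | 0.779 | 0.820 |
| 0.283 | 10% | 7.43 | 0.748 | 0.791 |
| 0.571 (half persists: 0.5 + 0.5 × 0.142) | 10% | 7.66 | 0.773 | 0.815 |
| 1 (all persists) | any | 8.00 | 0.808 | 0.847 |

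Two checks show how far these figures depend on the assumptions:

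- Allowing for the extra spread that late ratings create in the active arm, 10% late with r = 0.142 gives 0.722 at 19 per group instead of 0.735. A 25% late share gives 0.578.
- The primary outcome is a change, while 8.48 is an SD of scores. With an assumed pre-post correlation of 0.7, the SD of change is 8.48 × √(2 × 0.3) = 6.57. Power at 19 per group then goes from 0.955 to 0.938 (5% late) or 0.916 (10% late) for r = 0.142.

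**The case against.** The strongest reply is that no error is shown. A ±7-day window contradicts nothing in the plan, and both inputs needed to show harm are missing. In 21 active patients, 5% to 10% late is one or two people. This stands: it limits the point to an improvement and the power figures to illustration.

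A second reply is that the gap rests on silence. Nothing says patients must stop on day 63 if the visit slips, the number of pills dispensed is not stated, and accountability is referred to a Manual of Operations that is not among the documents. On-Study Evaluations also asks for rating scales at discontinuation, though this most naturally concerns those who stop early. These possibilities cannot be excluded, but a window set in the protocol is best settled there.

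Third, the primary analysis is intent-to-treat, so late ratings stay in it and relabelling them as deviations removes no dilution. That is right: only visits that actually move help. Ratings after early stopping are a consequence of treatment and belong in the comparison. A delayed visit in a patient who completed the course is an avoidable artefact.

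A reader might also infer that the primary outcome is measured off drug in everyone, taking eight weeks as total treatment. Dosing would then end on day 56 and the nominal visit would fall seven half-lives later. The documents do not support this: the two intervention sections count 63 days, and eight weeks can be read as counted from full dose. The text does not say so, however, which is why the wording needs reconciling.

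**Conclusion.** The point holds as an optional improvement. With 63 scheduled dosing days and a blanket ±7-day window, a compliant primary rating can come up to about seven days after the last scheduled dose. This rests on the nine-week reading and on there being no provision elsewhere for dosing to a delayed visit.

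The consequence is unknown and may be nil. Any dilution requires both that some visits run late and that a balance effect fades within days. A reader might infer from the table that the trial stands to lose a definite amount of power. It does not show that, because the late shares and fading rates are assumed and the SD is cross-sectional. Only the direction is firm: any effect of late ratings is toward no difference.

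**What to change.** 1. Give the final visit its own window, still opening seven days early but closing at the last scheduled dosing day, in place of the general ±7 days. A rating the next morning can be treated as immaterial.
2. Book the final visit at entry and confirm it at the existing call, when subjects already are due a contact: "they will be contacted by phone at week seven to assess for safety and tolerability".
3. Record the date of last dose on the CRF. Pill counts and adherence questionnaires are already collected, but the documents do not name this date as an item.
4. Keep any late ratings in the intent-to-treat primary analysis. Label any analysis by time since last dose as exploratory, because it selects on a post-randomisation variable.
5. Reconcile the eight-week wording (Interventions and Duration, Primary Objective, Secondary Objectives) with the nine-week wording (the two intervention sections, Concomitant Interventions, Timing of Evaluations), so that the last scheduled dosing day is fixed. No dose or course length is proposed here.

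The cost is one line on the window, one CRF field, one item on an existing call and a wording check; no extra patients or visits are needed. The downsides are tighter scheduling of one visit, somewhat more ratings before day 63 (already allowed from day 56), and more recorded visit-window deviations.

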### Special Instruction and Definitions of Evaluations

The source document will include all of the following listed below:

- Informed Consent: The patient will have an opportunity to review the consent form and ask any questions prior to signing the form. If the patient has dementia, he/she will be excluded from the study. A copy of the signed consent form will be given to the subject, and copies will be maintained in the study chart and the hospital record.
- Documentation of PD: Diagnosis of PD will be documented in the patient's chart prior to study entry.
- Medical History: The subject's history regarding PD will be obtained or a record of this history will be secured for the study chart. A complete social history, family history, and review of systems will also be performed.
- Treatment History: Allergies will be reviewed. Prior and current medications and other treatments will be reviewed and documented.
- Clinical Assessments: Clinical assessment procedures will be reviewed at the entry visit and the neurological examination will be performed. Clinical assessments to review safety, tolerability, and effectiveness will be conducted at each face-to-face visit or over the phone. Neurological examination will occur at the face-to-face visits only. Change in neurological signs or symptoms, adverse events, or tolerability issues should be recorded on the CRFs.
- Laboratory Evaluations: Blood chemistry and hematology will be performed and the resulting laboratory result forms will be placed in the study record.
- Questionnaires and Rating Scales: Scoring for each item on the Berg Balance Scale will be recorded in the scoring grid. Scoring for the MDS-UPDRS, TUG, ABC,

MMSE, Beck Depression Inventory, Beck scale for suicidal ideation, and FAB will be recorded in the CRF.

- Adherence Assessments: Pill counts and questionnaires will be filled out at every phone or in-person visit.

#### **Off-Intervention Requirements**

Recording of adverse events for subjects after the study will occur in the setting of regular care with the treating neurologist.

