The dosage escalation medication regimen in this protocol is similar to those studies conducted for smoking cessation and for ataxia. The active medication will be dosed twice daily (1 mg BID) due to convention, though the half-life of the drug is listed as 24 hours. A week of dose escalation will allow for maximal tolerability. The worsening of neuropsychiatric symptoms reported in some patients with other disorders on varenicline appears to be isolated in patients with prior psychiatric conditions, but this has not always been the case. In order to monitor for this potential side effect and to screen for potential sub-clinical depression, the Beck Depression Inventory will be given to all subjects and followed during the course of the study. Suicidal ideation and attempt has also been reported in patients taking varenicline, so the Beck Scale for Suicidal Ideation will also be administered to participants during the course of the study. There are no aspects of the proposed dosing schedule that are not FDA-approved for other indications. This study is

of high priority due to the absence of any proven medications to treat imbalance in this disorder.

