#### Study Enrollment Procedures

Patients with Parkinson Disease (PD) will be recruited through the Movement Disorders clinic located at the Neuroscience Institute at Rush University Medical Center. There are eight movement disorders attending physicians and three fellows who see approximately 4800 new and follow-up PD patients per year. Recruitment goals are expected to be predominantly achieved through the cohort of individuals seen at Rush, but advertising may also be conducted through monthly PD support group meetings or newsletters to enhance enrollment. Potential subjects may be identified by their treating physician in the Movement Disorders Clinic at Rush or referred to Rush from elsewhere. If a patient is interested in enrolling in this study, he/she will be invited to an initial study visit, at which time he/she will provide informed consent after a full explanation of the study.

Documentation of inclusion and exclusion criteria will occur if the patient is interested in enrollment. Eligible subjects who refuse participation will be given the option of later enrollment if desired.

Much of recruitment will occur from physicians who have a treatment relationship with the patient. Prior to the consent process, the Mini Mental State Examination will be performed to determine the patient's level of comprehension. If the potential subject scores less than 25, the patient will be excluded from the study. Consent will be obtained by the primary investigator and the potential subject. All investigators are trained in the conduct of human research. A copy of the consent form will be provided to all subjects.

The independent medical monitor will be responsible for obtaining group assignments. The assignment will be masked to the PI, the treating physician, the

subject, and all other staff conducting the study. The medical monitor will be responsible for correct drug dispensing for each subject based on randomization.

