#### **CRITERIA FOR INTERVENTION DISCONTINUATION**

Criteria and rules for stopping subject treatment include: new toxicological findings or serious adverse events, patient withdrawal of consent without need for justification, inability of the patient to participate for medical reasons (such as surgery), violation of eligibility criteria, development of significant neuropsychiatric symptoms such as suicidal ideation or psychosis, subject failure to comply with the protocol, development of cardiovascular symptoms, new cardiovascular diagnosis, or a cardiovascular event. Subjects who stop treatment will still be asked to complete a final visit with rating scales and blood work.

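### No planned trial contact covers the days just after the last dose, and adverse events noted then have no stated route into the trial record

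*Combined protocol and SAP*

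**What the plan says.** - **Off-Intervention Requirements:** "Recording of adverse events for subjects after the study will occur in the setting of regular care with the treating neurologist".
- **The Handling of Study Interventions:** after three days on one pill a day, the supply is "two pills daily for the next four days, then two pills of 1 mg for the remaining 56 days". Interventions, Administration, and Duration (eight weeks after the escalation week) and Concomitant Interventions (a nine-week study) agree with this. The synopsis section, Interventions and Duration, gives eight weeks on drug before reassessment.
- **Timing of Evaluations:** "They will be seen at nine weeks and outcome measures will be performed". Week 9 is the last column of Table 1.
- **Rationale:** "the half-life of the drug is listed as 24 hours".
- **On-Study Evaluations:** visits may move by 7 days either way. After the intervention the section offers only standard-of-care neurological examinations, by a treating neurologist or investigator.
- **Adverse Experience Reporting:** events are reported within three days and serious events within 24 hours. No end of the reporting period is given, and details are left to the Manual of Operations.
- **Subjects who stop early:** On-Study Evaluations lists assessments at discontinuation. Criteria for Intervention Discontinuation adds: "Subjects who stop treatment will still be asked to complete a final visit with rating scales and blood work". The phone contacts in Timing of Evaluations are introduced with: "Once on the study medication, they will be contacted by phone at three weeks".

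**The concern.** During the study, adverse events have a defined path. They are recorded on the case report form at visits and calls, and sent to the medical monitor. Off-Intervention Requirements replaces that path with routine care once the study ends, and under the dispensing schedule the study ends at about the moment dosing does. Followed as written, the trial collects almost no off-drug safety data on subjects who complete treatment.

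This matters because the protocol itself names the risks. It cites reports of suicidal ideation and attempt, promises strict monitoring of psychiatric effects, and stops treatment for neuropsychiatric and cardiovascular events. No interim safety analysis is planned, and the stopping guidelines depend partly on serious events reported from subjects on active drug, so the monitor depends on events being passed on. Aim 3 compares adverse events between arms, which needs one stated collection period. The neurologist who sees the subject afterwards could be outside the study team, since candidates may be "referred to Rush from elsewhere", although most are expected to come from the site's own clinic.

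**Working it through.** **1. Length of dosing.** From The Handling of Study Interventions: 3 + 4 + 56 = 63 days. This reproduces the nine-week duration in Concomitant Interventions, since 9 × 7 = 63.

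**2. Planned time from last dose to last contact.** Week 9 visit at day 63, minus last dose at about day 63, gives about 0 days. With the ±7-day window the visit falls between day 56 and day 70, so the gap runs from −7 to +7 days.

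**3. Drug remaining after the last dose.** Assume simple first-order elimination at the listed half-life of 24 hours. The share of the end-of-dosing level left after k days is 0.5^k.

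| Days after last dose | Share remaining |
|---|---|
| 1 | 50% |
| 2 | 25% |
| 3 | 12.5% |
| 5 | 3.1% |
| 7 | 0.8% |

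Taking five half-lives as the end of washout (a convention, not a figure in the protocol), washout lasts about 5 days.

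**4. How much of the washout a trial contact covers.**

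| Case | Last dose | Last contact | Days off drug at last contact | Share remaining then |
|---|---|---|---|---|
| Dispensing schedule, visit on time | day 63 | day 63 | 0 | 100% |
| Dispensing schedule, visit 7 days late | day 63 | day 70 | 7 | 0.8% |
| Synopsis, if its eight weeks include escalation, visit on time | day 56 | day 63 | 7 | 0.8% |

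The gap is therefore about 5 days on the reading that most sections support. It closes if the visit is a week late, or if the synopsis is read as 56 days in total.

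**5. Route into the trial record.** Special Instruction and Definitions of Evaluations ties case report form entries to face-to-face or phone contacts, and none is scheduled after Week 9. Off-Intervention Requirements names who records later events. It does not say for how long, on what form, or how they reach the monitor or the Aim 3 comparison.

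**6. Subjects who stop early.** The timing of their final visit is not stated. If it coincides with the discontinuation evaluation, planned off-drug observation at that visit is 0 days. If it is at Week 9, a subject who stops in week 2 is seen about 9 − 2 = 7 weeks later. Whether the Week 3, 5 and 7 contacts apply in between is also not stated.

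**The case against.** The strongest reply is that off-study recording is a stated design choice and that several provisions shrink the gap. The later clinician may be the investigator. Serious-event reporting has no stated end, so it may continue after Week 9. The Manual of Operations may set out a route that we cannot see. A late visit within the window covers the washout, as does one reading of the synopsis. The half-life supports a gap of only about five days and does not show how late a psychiatric or cardiovascular event could occur. All of this stands and limits the size of the point. None of it supplies a collection period or a planned contact after the last dose, and coverage through a late visit would be chance.

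A reader might also infer three stronger things that the documents do not support:

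- **That late events are lost.** Routine care is named as the place of recording. What is missing is a stated path from there into the trial.
- **That recording ends earlier for subjects who stop treatment.** The rule applies after the study, not after the drug. If their final visit is at Week 9, they are observed off drug for longer than completers. The wording that introduces the phone calls most naturally marks when contacts begin, not when they end.
- **That the loss falls mainly on varenicline.** No discontinuation rates by arm are given, both arms follow the same schedule, and the protocol lists the same four commonest side effects for placebo.

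**Conclusion.** The point holds as a gap in planned safety follow-up. On the dispensing schedule, a washout of about 5 days after the last dose has no planned trial contact, and no stated route carries events from that time to the case report form, the monitor or the Aim 3 comparison.

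This rests on 63 days of dosing, a Week 9 visit held on time, the listed 24-hour half-life with first-order elimination, and the five-half-life convention. It also rests on the supplied documents alone, since the Manual of Operations may add detail. The primary outcome and the sample size are unaffected. The change is worth making because it is cheap and serves risks that the protocol says it will monitor.

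**What to change.** Change Off-Intervention Requirements so that the study team collects adverse events over a defined period after the last dose, the same in both arms. The sponsor should set the length and justify it against the half-life it lists. One phone contact per subject by existing staff is enough. Record the events on the case report form, send them to the medical monitor, and add the contact to Table 1. State in Adverse Experience Reporting when collection of adverse and serious adverse events ends, and in Aim 3 that the comparison covers that period.

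Separately, reconcile two sets of statements, whose content is for the sponsor to decide:

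- Interventions and Duration against The Handling of Study Interventions, on the length of dosing.
- Timing of Evaluations, On-Study Evaluations and Criteria for Intervention Discontinuation, on when the final visit of a subject who stops takes place and which scheduled contacts apply.

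The cost is a protocol amendment, up to 42 calls, and a slightly later database lock if the last subject's contact falls after the planned date.
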